### 3.1 Study design and procedures

Infants will be eligible for xenon if the St Michael's hospital standard inclusion criteria for cooling are met and additional inclusion criteria for xenon administration are met.

#### St Michael's hospital standard inclusion criteria for cooling:

Standard Hypothermia Treatment Criteria for 72 hrs of cooling — all of criteria A, B, and C.

A Infants  $\geq$  36.0 weeks gestation (estimated or clinical assessment) with at least ONE of the following:

- 1 Apgar score of  $\leq$  5 at ten (10) minutes after birth
- 2 Continued need for resuscitation, including tracheal or mask ventilation, at ten minutes after birth
- 3 Acidosis defined as either umbilical cord pH or any arterial, venous or capillary pH within 60 minutes of birth less  $<$  7.00
- 4 Base deficit  $\geq$  16 mmol/L in umbilical cord blood sample or any blood sample within 60 minutes of birth (arterial or venous blood). If the infant meets criterion A then assess for neurological abnormality using criterion B and C (by trained personnel):

B Moderate or Severe encephalopathy as evidenced by any of the following --

- 1 Altered state of consciousness (reduced or absent responses or pathological irritability and hyper responsive and at least ONE or more of the following:
- 2 Hypotonia
- 3 Abnormal reflexes including oculomotor or pupillary abnormalities
- 4 Absent or weak suck
- 5 Clinical seizures, as recorded by trained personnel

*And*

C At least 30 minutes duration of amplitude-integrated electroencephalography (aEEG) recording that shows abnormal background aEEG activity. The decision to cool is based on the worst 30 min section of the aEEG, not the best [35] or seizures (clinical or electrical) thus meeting ONE of the following:

- 1 Normal background with some ( $>$  5 min) electrical seizure activity
- 2 Moderately abnormal activity (upper margin of trace  $>$  10  $\mu$ V and lower margin  $<$  5  $\mu$ V)
- 3 Suppressed activity (upper margin of trace  $<$  10  $\mu$ V and lower margin of trace  $<$  5  $\mu$ V)
- 4 Definite seizure activity

#### Exclusion criteria for cooling in the CoolXenon2 study

1. Infants expected to be greater than 3 hours of age at the time of starting cooling treatment.
2. Futility. Where prognosis is considered to be hopeless e.g. no cardiac output for 20 minutes.

#### Additional inclusion criteria for xenon

Before being considered for additional inhaled xenon therapy via the breathing gas mixture, the infant would need to meet further additional entry criteria (all must be met):

- 1) Intubated, ventilated, sedated, being cooled.
- 2)  $<$  5 hours old
- 3) Any seizures under control.
- 4) Weight  $>$  2nd centile for gestational age
- 5) Stable cardiovascular parameters; Mean arterial pressure  $>$  40 mmHg.
- 6) Oxygen requirement via mechanical ventilator  $<$  40%.
- 7) Positive End Expiratory Pressure (PEEP) requirement  $<$  6 cm H2O
- 8) Arterial/capillary/venous pCO2  $<$  7.0 kPa (ideally arterial). Venous can be higher if peri-arrest and tissues have been very recently ischaemic
- 9) Postnatal age  $<$  5 hours
- 10) Absence of major congenital abnormalities, imperforate anus and in particular any bowel obstruction, congenital abnormalities suggestive of chromosomal anomaly or other syndromes that include brain dysgenesis. Congenital syndromes affecting the brain should be excluded when diagnosed.

Reference:	CH
Issue:	2
Revision:	3
Issue Date:	1 May 2013
Page	17 of 49

## Consent

Informed written consent will be obtained from a parent (only the mother can consent if parents are not married) after a full verbal and written explanation of the study by a named physician or trained nurse like an advanced nurse practitioner. Such staff will also meet with parents during the intervention period to ensure that they understand the study procedures and continue to consent to participate in the study. Information can be given by local trained staff and consent can also be taken over the phone with the mother if she is unable to be available for the consent process (e.g. cannot be moved shortly after Caesarean Section).

Approval for the study is being obtained from the Regional South West Research Ethics Committee covering St Michael's Hospital.

Most of the patients will be born outside the study hospital (Outborn). Outborn patients are estimated to be >90% of patients. They are brought to the hospital by a dedicated retrieval team and ambulance from Bristol.

The local delivery hospitals will have medical staff (e.g. consultants, specialist registrars, advanced nurse practitioners) trained in consenting for the CoolXenon2 trial. A training log with signatures, a short CV and competency approval will be kept centrally.

Parents will receive a written information leaflet (1 page, short version) when the infant is eligible for cooling treatment. Staff will discuss CoolXenon2 with parents as soon as practically possible. Parents will be able to speak on the phone to a member of the treatment team if they need further information and help with the consent process.

Parents will also be offered the opportunity to speak to members of the treatment team that are picking up the baby for transport.

Trained staff on the transport team can take consent for the study.

A more detailed information sheet regarding the trial will be given to parents after the first conversation or at the earliest suitable time.

### Which of the parents can consent to letting the child enter the trial?

- Either parent if they are married.
- If the parents are not married, only the mother can consent - provided she is awake and understanding (eg not under the influence of anaesthetic drugs)

If the mother is not in a state to understand the situation and the biological father does currently not have legal parental responsibility he can assent for the trial until the mother is awake/understanding the child's condition and able to decide on consent.

A parent who is eligible to consent can, at any time and without a specific reason, withdraw the child from the study. In this situation, xenon treatment will then be stopped as soon as possible and medically safe (within minutes).

## Randomisation

The babies entered into the study will be randomised into two groups on a 1:1 basis. Randomisation will be via sealed opaque envelopes containing details of treatment allocation and [an] identifying adhesive label(s) to be attached to the CRF binder. Neonates meeting all the entry criteria can be included. In this study early randomisation before 5h of age is paramount. The maximum target delay before starting cooling is before 3h of age and for xenon this value is 5h of age. These are maximum delay values however so consent and randomisation need to take place as early as possible.

## Clinical management

- 1) The neonates would be sedated, mechanically ventilated and cooled according to the protocol for cooling listed above, as this is standard treatment. In the case of retrieved babies, cooling is always started before transfer to Bristol (active or passive cooling). If not before, active cooling starts when the transport team arrives. Antibiotics, fluid management and sedative drugs used would be unmodified.
- 2) Neonates would be entered into the study according to the set criteria within a maximum of 5hrs of birth with respect to adding xenon to the existing underlying standard cooling regime which has started within 3 hrs (passive or active).

Reference:	CH
Issue:	2
Revision:	3
Issue Date:	1 May 2013
Page	18 of 49

*Specific clinical management of cooling group*

1. This group will be cooled according to the normal protocols of the hospital as this is standard treatment.

*Specific clinical management of xenon+cooling group*

After initial resuscitation and attainment of a stable state, and inclusion in the study, the tracheal tube would be replaced with a cuffed commercially available tracheal tube (Kimberley-Clark microcuff) of the same or 0.5mm smaller size as the existing one and the cuff inflated until leakage of gas around the cuff had ceased audibly and according to the ventilator monitor. This particular tube has a high volume, low pressure cuff and is specifically designed for long term use on the paediatric or neonatal intensive care unit. The cuff pressure will be monitored and recorded at the time of initial inflation, during xenon administration every 2 hours and just prior to final deflation. If there are any post extubation adverse events such as stridor, or extubation fails secondary to vocal cord, nerve or subglottic damage, these will be recorded. The experience from our recent neonatal feasibility/safety study was that of the 14 babies, one baby developed post-extubation stridor requiring steroids. \* See Appendix 4.

\*In a recent very large study of cuffed tracheal tubes for anaesthesia in infants and neonates, the use of a cuffed tube did not increase risk of post-extubation stridor. In 2246 children, post-extubation stridor was noted in 4.4% of those with a cuffed tracheal tube and 4.7% of those with uncuffed tubes, with a much lower tube exchange rate in the cuffed tube group. See Appendix 11.

1. The dose (fraction of xenon in breathing gas) planned for each patient in the xenon+cooling group will be 50%. It will be applied for 18 hours. It will be commenced as soon as is practicable but no later than 5h after birth once all the entry criteria / consent requirements have been met.
2. If a baby is being retrieved from another local hospital to the study centre (Bristol) using the existing Bristol-provided retrieval team and ambulance, AND they have been consented and randomised to receive xenon AND if it is deemed probable that the delay between birth and the start of xenon in Bristol would exceed an interval of 5 hours, then if logically possible an assigned research team member will accompany or meet the retrieval team and commence xenon delivery at the local hospital or during the return transfer of the baby to Bristol.
- 3) Full data sets will be acquired in two groups of 16 patients. The mortality rate in the patients referred for cooling to Bristol is ~25%.
- 4) Cooling will be for 72 hours using the clinically chosen cooling device in both groups, as is current standard practice for cooling.

**Further information on the oxygen fraction in the breathing gas mixture**

The Xenon we intend to use (LenoXe) is currently licensed for anaesthesia in adults. The LenoXe SmPC specifies that xenon should be administered (for adult anaesthesia) with at least 30% oxygen in the breathing gas mixture. It is our intention in this study to administer an oxygen fraction in the breathing gas to ensure adequate oxygenation of the blood of the neonate, but not to give an excess, as there is also a real risk of hyperoxic brain damage in this group of neonates if the oxygen fraction is too high. Consequently, in a neonate with normal lungs being sedated and ventilated for cooling rather than for any lung problems, the inspired oxygen fraction could equal that of air i.e. 21%. No neonate would ever receive less than 21% oxygen and the fraction delivered would be specific to each individual according to clinical need.

**Explanation:**

The reason the LenoXe SmPc specifies 30% oxygen is following the normal practice of anaesthesia using other gases and vapours, because during anaesthesia in adults the ventilation/perfusion mismatch in the lungs becomes very slightly less efficient than in the awake state. This is due to changes in muscle tone, diaphragm position/shape and effects of

Reference:	CH
Issue:	2
Revision:	3
Issue Date:	1 May 2013
Page	19 of 49

gravity on distribution of blood flow through regions of the lung. This is why although humans are designed to breathe air (21% oxygen), under anaesthesia in someone with normal lungs we would traditionally use approximately 30% oxygen (more if there were any lung problems as clinically indicated).

It should be noted that this anaesthetic tradition to use a slightly higher inspired oxygen fraction than might strictly be required developed before it became commonplace and later mandatory to use pulse oximetry to continuously monitor oxygen saturation of the blood and end-expired carbon dioxide monitoring to continuously monitor the adequacy of ventilation (in terms of carbon dioxide removal from the blood) which became widespread in the late 1980's / early 1990's.

In the neonates of this study the situation is different as they have all recently suffered a hypoxic-ischaemic (HI) insult to the brain and other organs around birth. Ventilating them with a gas mixture containing an oxygen fraction even slightly higher than necessary is considered highly undesirable as in this situation it can actually worsen the subsequent brain injury. This explains recent changes to resuscitation equipment for the newborn where the 100% oxygen supplies have been replaced with air/oxygen blenders. The new ILCOR Resuscitation Guidelines [37] state that term newborns should first be resuscitated in air, then with a higher concentration of oxygen if pulse oximetry or clinical signs suggest poor oxygenation.

i) It is worth noting that regional variations in ventilation/perfusion throughout the regions of a healthy neonatal lung are less affected by anaesthesia/sedation than in a (much larger) adult so the physiological (anaesthetic) justification for automatically using 30% oxygen is weaker in the neonate.

*However the more relevant points with respect to this study are:*

ii) While in anaesthesia practice it may be normal and quite harmless to set an inspired oxygen fraction slightly higher than strictly necessary, in neonates that have suffered a hypoxic-ischaemic insult to the brain and other organs around birth, it is considered **highly undesirable** to administer an inspired oxygen fraction that is any higher than the amount required for adequate oxygen delivery to the organs. We have recently shown experimentally that 30 min of 100% oxygen after hypoxia-ischaemia increased injury [38].

iii) Consequently,

- we monitor *oxygen saturation of the blood* of the neonate using continuous pulse oximetry (with audible and visual alarms),
- we continuously monitor *adequacy of ventilation* with a neonatal end-expired carbon dioxide monitor which reflects the systemic arterial carbon dioxide content. While mandatory in adult intensive care practice this is not yet the case in neonatal practice due to unavailability of suitable monitors for neonates, a situation which is now changing.
- We also routinely monitor oxygen saturation of the blood periodically in ventilated neonates by analysing arterial blood samples using a blood gas analyser. In neonates that have experienced an HI insult around birth the attending physicians are not only checking that the oxygen content is not too low but also *they are checking it is not too high*. A slight elevation that would normally be acceptable is not acceptable in this particular group of babies and if too high they will actively request that the inspired oxygen fraction in the breathing gas be reduced.
- As a result of the above, *the inspired breathing gas might contain a theoretical maximum oxygen fraction of 40% as stated in the protocol if clinically required due to lung problems, but also this may for the above reasons be deliberately set as low as 21% (as in room air) if the lungs are normal.*

The desired inspired xenon fraction is to be set at 50% as per the protocol. The "balance gas" in situations where a moderate oxygen fraction is being used will be nitrogen. This will simply be room air which although containing 21% oxygen is otherwise mainly composed of nitrogen.

### Vigilance and monitoring

This would be ongoing during every case. It would include

- Blood gases 2 hourly or as clinically requested up to 1 hourly.
- (cardiac echo /doppler) where available
- Blood Pressure

Reference:	CH
Issue:	2
Revision:	3
Issue Date:	1 May 2013
Page	20 of 49

- Heart rate
- Oxygen saturation by pulse oximeter SaO2
- Xe concentration and O2 concentration in gas mixture
- End Tidal CO2 (ETCO2) (Respironics mainstream monitor with very low deadspace in neonatal connection)

#### Action to be taken with respect to typical problems in this patient group

- 1) Hypotension or inadequate cardiac output: 10ml/kg 0.9% Saline (or occasionally 4% human albumin or blood) as required (x2).

Dopamine infusion commenced (up to 20mcg/kg/hr) followed by Dobutamine (up to 20mcg/kg/hr), then Hydrocortisone up to 2.5mg/kg 6 hourly or other inotrope as indicated.

If not effective then Xe delivery is stopped and conventional ventilation/gas mixture resumed.

- 2) Low SaO2 or low oxygen partial pressure on blood gas analysis:

Increased oxygen fraction in breathing gas mixture as required up to maximum of 40%.

If not effective, then Xe delivery stopped and conventional ventilation/gas mixture resumed. If reason for high FiO2 is easily solved, e.g. improved by surfactant delivery or changed ventilation settings or clearing a blocked tube, then xenon can be resumed.

- 3) High End-Tidal CO2 or CO2 partial pressure on blood gas analysis:

Increase peak pressure and/or breathing rate settings on mechanical ventilator.

If not effective then Xe delivery stopped and conventional ventilation/gas mixture resumed. This is readily achieved by disconnecting the ventilator hoses from their point of attachment to the xenon breathing system and connecting them directly to the tracheal tube of the neonate.

At the end of the prescribed period of Xe delivery the tracheal tube would be reconnected directly to the mechanical ventilator and normal ventilation and gas mixtures set as clinically appropriate. The cuff of the tracheal tube would be deflated. This tracheal tube would be replaced with an uncuffed tube at a later timepoint as clinically indicated or kept until the patient was extubated after rewarming. Cooling regimes last for 72hrs before slow rewarming commences (0.1-0.4°C per hour). The standard cooling protocol would continue for many more hours after cessation of the additional xenon regime.

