#### Potential risks from breathing system:

We are using a new breathing circuit to deliver this gas. This has been developed over many years by a Consultant Anaesthetist who is a co-researcher on this team and world leader on this subject. It has been tested extensively in laboratory neonatal pig simulations of the condition (see section 4.3.1). To minimise risk of any technical problems:

- i) The equipment design is being evaluated for safety by the MHRA. It will be professionally constructed from all medical grade materials.
- ii) The design is such that the xenon system is placed between the standard mechanical ventilator and the baby. This means that if there is any technical problem, the ventilator can be immediately connected directly to the baby and the xenon system removed in one simple intuitive operation.
- iii) The gas composition, in particular oxygen, of the circuit gas will be continuously measured, as will xenon and the end-tidal carbon dioxide (which reflects the arterial value).
- iv) The breathing system has an overpressure release valve in the event of any mishap.

Reference:	CH
Issue:	2
Revision:	3
Issue Date:	1 May 2013
Page	22 of 49

- v) Furthermore if there were any problem due to the xenon gas itself, reconnection directly to the ventilator would also allow all the xenon to be breathed out from the baby within a few breaths, i.e. the xenon treatment is rapidly reversible. Finally:
- vi) The xenon will be delivered by trained personnel who have also been involved with laboratory trials using xenon in animal models
- vii) The possibility of interaction between the xenon gas and the materials of the breathing circuit has been considered. As xenon is chemically "inert" i.e. does not form chemical compounds except in the most extreme circumstances, there is no perceived risk.
- viii) A full risk assessment in accordance with standard medical device regulatory requirements has been undertaken and thoroughly documented

This design of breathing system has now been evaluated in this same patient population as in our recently completed 14 baby human feasibility/safety study. The findings are summarised in Appendix 4.

Use of cuffed tracheal tube:

After onset of cooling and attainment of a stable state, the tracheal tube would be replaced with a cuffed commercially available tracheal tube (Kimberley-Clark microcuff) of the same or 0.5mm smaller size as the existing one.

To minimise the gas pressure in the cuff:

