## 4.0 Study Therapies

### 4.1 Test Article: Description

#### Overview

The neonatal xenon breathing device (NXBD) is a gas delivery circuit with some similarities to an anaesthesia circuit that is temporarily placed between a standard mechanical ventilator and the tracheal tube of a neonate to deliver xenon as a therapy in the breathing gas. It is designed for use in neonates who already require mechanical ventilation in this manner on a neonatal intensive care unit. Its purpose is to provide a gas mixture to the lungs that contains not only an appropriate oxygen concentration to maintain life, but also to provide a concentration of up to 50% xenon in this mixture. The reason for this is that xenon shows great promise as a neuroprotectant and has been shown to reduce neurological damage in both small and large laboratory *in-vivo* models of neonatal hypoxia-ischaemia (birth asphyxia for example). By re-circulating the exhaled gases after removal of carbon dioxide then, as the uptake of xenon by a neonate is very low and the system does not "vent" any exhaled gas to the environment, it provides a very economical method of xenon delivery. Such economy will be essential for any future clinical use of xenon as this gas is both limited in availability and extremely expensive at approximately £20/litre. While the (minimal) xenon uptake is replaced manually by the operator, the breathing device automatically adds oxygen as required to match metabolic uptake by the patient. This is not achieved by complex sensors and electronics but by a straightforward mechanical mechanism for reliability. Furthermore, if xenon replacement is stopped, the inspired oxygen concentration will tend to very slowly increase i.e. it will not fall as the patient consumes oxygen from the circuit – these are both inherent safety features. The most important and intuitive safety feature is that in the event of any problem, the mechanical ventilator patient connector can be disconnected from the breathing system and reconnected directly to the tracheal tube of the neonate, instantly restoring normal ventilation and also allowing any xenon to very rapidly dissipate from the tissues of the neonate.

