### 4.2 Test Article: Principles of Operation

If no fresh oxygen is supplied to a conventional anaesthesia circle system the patient will consume all oxygen present until a hypoxic mixture develops. Therefore in a closed circle system, fresh gases must be added at a rate exactly matching patient uptake of each gas. There are various ways to achieve this. In the simplest of closed underwater diving systems, the user will breathe pure oxygen around a circuit similar to an anaesthesia circle. In time, by metabolic oxygen consumption, the reservoir bag will completely collapse part-way through an inspired breath. At this point, by continued inspiratory effort, a demand valve on an attached oxygen cylinder will open, providing the missing volume of oxygen to complete the inspiration phase. If we now imagine this circle to contain a mixture of xenon (slow patient uptake) and oxygen (metabolic uptake) a different situation develops. It can be envisaged that substitution of these two uptake volumes with pure oxygen at each end-inspiration would produce a slowly increasing inspired oxygen fraction ( $FiO_2$ ).

[figure not shown]
We have incorporated these concepts into a ventilator driven closed circuit where a standard Neonatal Intensive Care Unit (NICU) ventilator, set to deliver 100% oxygen in each breath to the circuit, provides not only the motive power but also, via a special volume substitution valve, the required oxygen replenishment in place of the demand valve in the diving example.

Reference:	CH
Issue:	2
Revision:	3
Issue Date:	1 May 2013
Page	26 of 49

When delivering a xenon/oxygen mixture there would then be a background tendency for the  $\text{FiO}_2$  to slowly increase while the inspired xenon concentration decreases at a similar rate. This provides a degree of hypoxic mixture protection without use of oxygen sensor and computer software controlled electronic valves. In other words, adequate oxygen supply, the most critical function of any breathing system, is not entirely dependent on correct functioning of sensors, software and electronic dosing valves, as would be the case with an electronically controlled system.

[figure not shown]

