Against this inherent safety feature of a very slowly increasing the  $\text{FiO}_2$ , and the minimal xenon uptake of a neonate from the closed loop circle breathing system, xenon can then be delivered to the circle in small volumes under manual control to offset this trend, replacing the minimal patient xenon uptake.

The design of a breathing circuit to achieve these design aims is described in Figure 1.

**Figure 1a.** Diagram of the breathing system

Reference:	CH
Issue:	2
Revision:	3
Issue Date:	1 May 2013
Page	27 of 49

**Figure 1b.** Views of breathing system (without hoses)

[figure not shown]
The xenon delivery system is designed to be fitted between a conventional neonatal intensive care unit (NICU) mechanical ventilator (SLE 2000, SLE, South Croydon, UK) and the tracheal tube. The latex-free bag in the lower chamber has a volume of 500ml, larger than a neonatal tidal volume, providing free space to accommodate added xenon bolus volumes without overspill. The removable soda-lime canister has a volume of 510ml permitting long periods of ventilation without replacement.

In this design, a small aliquot of oxygen enters the closed circle upper part of the circuit at each end-inspiration from a lower bag-in-bottle chamber (where it is present as the driving gas from the ventilator) via a dedicated oxygen substitution valve. Modern NICU ventilators maintain a bias gas flow throughout the breathing cycle. At end-expiration this displaces any residual CO2 from the "Y" connector reducing CO2 rebreathing. However with a closed circuit, the absence of a bias flow combined with small neonatal tidal volumes means that an efficient self-closing, leak free, low opening pressure inspiratory valve was required to prevent rebreathing. A unidirectional valve performs this function. A similar valve design is used as the expiratory valve and as the oxygen substitution valve.

Gas delivery to breathing system:

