**Figure 2.**

A flexible bulb and valve arrangement allows manual addition of ~50ml xenon boluses to the circle breathing system, from a previously filled reservoir bag of xenon at ambient pressure. These are added to the expiratory limb of the circuit to allow maximum mixing with existing gases in the circle before entering the lungs. The small flexible bulb volume of 50ml was selected because the small bulb volume combined with its slow refill properties further aids even gas mixing, it being impossible to rapidly add a large xenon bolus. Erring on the side of caution, our circuit was primed with oxygen. The xenon/oxygen monitors are constantly observed as in the conduct of a conventional anaesthetic. Deviations in xenon concentration of more than 2-4% from target are corrected by the operator adding xenon to the circuit, each 50ml bolus typically producing a 2% increase in xenon concentration. These corrections offset the inherent tendency of this circuit design to generate a very slowly increasing oxygen concentration ( $O_2$  + minimal Xe consumptions being replaced with equal volume of oxygen via substitution valve).

The overall design aims were that this breathing system should (i) be driven by a standard NICU ventilator, (ii) have inherent hypoxic mixture prevention properties not dependent on electronics (iii) provide the user with the most intuitive treatment reversal method; reconnection of the neonate directly to the NICU ventilator. It performs all these functions.

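### At an unplanned stop of xenon, moving the hoses is said to restore the conventional gas mixture, but the protocol has the ventilator set to 100% oxygen at that moment

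*Protocol*

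**What the plan says.** **How xenon is stopped.** Section 3.1 (action for typical problems) lists three reasons to stop xenon early: hypotension or poor cardiac output, low oxygenation, and high carbon dioxide, each where the first measures fail. Each item ends in a return to conventional ventilation and gas mixture. The third adds the means: "conventional ventilation/gas mixture resumed. This is readily achieved by disconnecting the ventilator hoses from their point of attachment to the xenon breathing system", the hoses then going straight to the tracheal tube.

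The same act is described in three other places:
- Potential risks from breathing system: in a technical fault, "the ventilator can be immediately connected directly to the baby and the xenon system removed in one simple intuitive operation".
- Section 4.1: the ventilator connector is "reconnected directly to the tracheal tube of the neonate, instantly restoring normal ventilation".
- Section 4.2, closing design aims: reconnection to the ventilator is the way treatment is reversed.

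**What the ventilator is set to.** Section 4.2 says that the ventilator is "set to deliver 100% oxygen in each breath to the circuit". It then describes oxygen in the lower chamber, "where it is present as the driving gas from the ventilator". During xenon the infant breathes the separate circle gas, not this drive gas.

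**What the protocol says about oxygen.** The explanation of the oxygen fraction in section 3.1 treats any oxygen above need as strongly to be avoided in these infants and describes an inspired range of 21% to 40%. It adds: "We have recently shown experimentally that 30 min of 100% oxygen after hypoxia-ischaemia increased injury".

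**Planned end of xenon.** The last paragraph of the same part of section 3.1 has the tube reconnected to the ventilator and the gas mixtures then set to clinical need.

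**The concern.** The protocol presents quick reversal as a key safety feature of the treatment. The written means of reversal is one mechanical act, and section 3.1 says that this act brings back the conventional mixture. On the protocol's own description of the ventilator setting, it does not. It connects the infant to a ventilator set to an oxygen fraction outside the described range, and of a kind that the protocol itself names as a hazard.

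The step is an urgent one. Since April 2013 xenon has also been started at referring hospitals and continued in the ambulance, where staff work away from the base hospital without the developer's supervision (section 3.3). The accuracy of the written steps matters more there.

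The written safeguards against excess oxygen do not clearly cover this moment. The continuous oxygen measurement in the breathing-system section is of the circuit gas, from which the infant has just been disconnected. The check that blood oxygen is not too high relies on blood gases, which are scheduled every 2 hours, or up to hourly on request.

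**Working it through.** The plan states no statistical figure on this point, so the check is a comparison of passages with simple arithmetic.

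**1. Does the stated means give the stated result?**
- Setting while xenon runs (section 4.2): 100% oxygen.
- Written act at an unplanned stop (sections 3.1, 4.1 and 4.2): move the ventilator from the circuit to the tracheal tube.
- Change of oxygen setting written into that act: none in any of the four places.
- Gas reaching the infant directly after the act as written: 100% oxygen, until someone changes the setting.
- Stated result (section 3.1): conventional gas mixture.

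The two do not match.

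**2. Size of the mismatch against the described range**
- Against the 40% maximum: 100 / 40 = 2.5.
- Against the 21% minimum: 100 / 21 = 4.8 (rounded).

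These are ratios of settings. The documents give no time for which the setting would stand, so no exposure can be calculated.

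**3. Could a reset be implied?**
The order to resume the conventional mixture implies that someone intends it. But the sentence on how this is achieved names only the hose change. The next paragraph, on the planned end, writes reconnection and the setting of gas mixtures as separate actions. The setting step is therefore explicit for the scheduled stop and absent from the unscheduled one.

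**4. To which stops does the conflict apply?**
- Hypotension, high carbon dioxide, equipment fault: nothing in the stated reason calls for more than 40% oxygen, so the conflict is clear.
- Low oxygenation: xenon is stopped because oxygen up to 40% has not been enough. A higher fraction may be what is needed, so the conflict is weaker.

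**5. Secondary: the circuit description**
- Target xenon: 50%. Described oxygen range: 21% to 40%, with nitrogen from room air as balance (section 3.1).
- Nitrogen needed at target: 100 − 50 − 40 = 10% at the upper end of the oxygen range, and 100 − 50 − 21 = 29% at the lower end.
- Section 4.2 describes only oxygen and xenon entering the circuit, and says of its preparation: "Erring on the side of caution, our circuit was primed with oxygen".
- With only those two gases, oxygen at target would be 100 − 50 = 50%, above the 40% maximum.

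Section 4.2 does not say how the 10% to 29% nitrogen gets in. Section 3.1 says that room air supplies it. The two accounts need to be joined.

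**The case against.** The strongest reply is that section 3.1 does order the conventional mixture resumed, in all three items, so leaving the ventilator at 100% would breach the instruction. The circuit is run by a team member with documented experience of it. Oxygen saturation is monitored continuously with alarms, and clinicians are told to watch for too much oxygen. A device risk assessment is said to exist but is not shown. The earlier study of 14 infants, with a system of the same design, reported no technical problems and no related adverse effects.

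Most of this stands. It makes a long exposure less likely and limits what can be claimed. It does not make the written means produce the written result.

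A reader might infer several stronger points, which the documents do not support:
- **That infants are harmed, or the comparison of arms is biased.** The cited evidence is experimental (the reference is a neonatal rat study) and concerns 30 minutes of 100% oxygen. No number of unplanned stops and no exposure time is given, and the analysis is descriptive. Any effect on the early outcome markers cannot be sized.
- **That every unplanned stop is affected.** The low-oxygenation stop is the exception already noted.
- **That all 16 planned xenon infants breathe more than 40% oxygen while the circuit fills.** The priming sentence is in the past tense, the figures are not shown, and section 3.1 gives nitrogen as balance gas. A count of boluses from the 2% per 50 ml in section 4.2 would also mislead, because that figure describes corrections near target.
- **That the circuit gas meets the criterion in section 8.3 for stopping xenon above 40% oxygen.** That text concerns an infant who comes to need high oxygen, not the gas used to prepare the circuit.

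**Conclusion.** The contradiction is real and lies in the protocol's own words. At an unplanned stop, the stated means does not by itself give the stated result, because the ventilator is described as set to 100% oxygen and no change of setting is written. The setting is 2.5 to about 4.8 times the described inspired range.

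This rests on two assumptions: that the setting in section 4.2 applies throughout xenon delivery, as the text indicates, and that no document outside this protocol adds the missing step. The duration and clinical effect are unknown from the documents.

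The point is therefore a conflict in a safety instruction that is cheap to correct, not evidence of harm or bias. The mismatch over the circuit gas is secondary: two descriptions to reconcile, not proof of exposure.

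**What to change.** Reconcile section 3.1 (action for typical problems), the section on breathing-system risks, section 4.1 and the design aims in section 4.2 with the ventilator setting in section 4.2 and the oxygen explanation in section 3.1. After the change, all should give one consistent account of the ventilator's oxygen setting at an unplanned disconnection. The clinical content is for the sponsor to decide. No oxygen value or clinical rule is proposed here.

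In the same revision, reconcile the circuit description in section 4.2 with the 40% maximum and the nitrogen balance gas in section 3.1, at the 50% xenon target.

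The cost is a change of wording in the protocol and in any bedside instruction drawn from it. Design, sample size and analysis are unaffected, and no new data item is needed, since the inspired oxygen fraction is already recorded under Endpoint 1 in section 2.2.
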